4.2 TREATMENT METHODOLOGY

MONTAGE will be used only at a focal site where the osteotomy is performed. It will be applied to the edges of the spine defect after removal of the wedge. MONTAGE will be applied immediately prior to placing the osteotomy site under compression prior to its hardening so as to ensure no interference with compression against the osteotomy edges. Participating investigators, at their discretion, may use autograft and allograft bone void fillers for the other parts of the spine fusion as part of standard of care.

A teaching video will be used to ensure strict adherence to the study procedure at all sites.

Hematological parameters, such as Hb, Hematocrit, RBC, WBC, platelet counts, MCV, MCHC, and differential counts will be recorded and compared between the groups at baseline, immediate post-surgery, and daily up until day 7 or discharge (whichever comes first).

All standard-of-care blood values, including CBC, electrolytes, liver function and kidney function tests during the initial hospital admission will be recorded and analyzed at certified laboratories.

Consistent radiographic parameters will be used to evaluate the angular measurements between the superior endplate of the vertebral body below the PSO and the one above it.

All radiographic images will be read by two reviewers, without knowledge of treatment groups (i.e., blinded).

The radiographic techniques that will be employed in this study are X-rays and CT scans of the thoracolumbar spine without contrast, focusing on the vertebral segments above the osteotomy, the osteotomy segment itself, and the spinal area just below the osteotomy procedure. All images during the study will be read by the same two reviewers.

4.2.1 Screening and Pre-Treatment Regimen

4.2.1.1 Visit #1: Screening Evaluation and Enrollment (Week -2)

- Signed written Informed Consent Form will be obtained.
- Subjects will be enrolled according to the Inclusion and Exclusion criteria listed above.
- Subject demographics, medical history, and vital signs will be recorded.
- A blood sample will be drawn from the subject for analysis of hematological and biochemical parameters at a central laboratory consistent with the study institutions preoperative workup
- Subjects will undergo pre-operative imaging using CT and radiographs, which are based on standard of care.
- Patient’s co-morbidities will be scored using the Charlson Comorbidity index, the ASA score as well as ISSG severity scores.

- A list of pain medications with dosing will be recorded
- VAS back and leg pain, ODIv2.1a and SRS-22 scores will be collected as a baseline.

4.2.2 Randomization

The randomization will occur with the participating center contacting the central study data repository after submitting preoperative subject data; random assignment will be generated by computer. Patients will be randomized to either PSO with MONTAGE or standard of care

4.2.3 Treatment

4.2.3.1 Visit #2: Treatment Phase (Week 0)

The patient will undergo the surgical intervention, excising a bone wedge from the vertebral body followed by a closure of the defect and re-apposition of the bony edges, creating the correction. Just prior to closure of the osteotomy, either MONTAGE or no bone hemostat will be placed on the surface of the cut bone.

Operative parameters, including surgery time (duration of surgery) level of the osteotomy and type of surgery, as well as intra-operative blood loss will be recorded.

The use of anti-fibrinolytics will be recorded.

Regular blood values, including Hb, Hematocrit, RBC, WBC, platelet count, MCV, MCHC and differential counts will be performed on each post operative day while subject is in the hospital, up until day 7.

Number of blood transfusions as well as any wound drain output will also be recorded.

4.2.3.2 Visit #3: Follow-up Visit (Week 2)

Radiographs- standing ap and lateral scoli xrays will be completed and centrally read by independent evaluators.

VAS back and leg, ODIv2.1a and SRS-22 scores will be collected.

Current Pain medications/dosing will be collected.

Adverse Events will be recorded.

4.2.3.3 Visit #4: Follow-up Visit (Week 6)

Radiographs- standing ap and lateral scoli xrays will be completed and centrally read by independent evaluators.

VAS back and leg, ODIv2.1a and SRS-22 scores will be collected

Current Pain medications/dosing will be collected.

Angular correction and gap will be measured.

Regular blood chemistry, including Hb, Hematocrit, RBC, WBC, Platelet count, MCV, MCHC and differential counts will be performed (as clinically indicated).

Adverse Events will be recorded

4.2.3.4 Visit #5: Follow-up Visit (Week 12)

Radiographs- standing ap and lateral scoli xrays will be completed and centrally read by independent evaluators.

VAS back and leg, ODIv2.1a and SRS-22 scores will be collected

Current Pain medications/dosing will be collected.

Work Status will be recorded

Angular correction and gap will be measured.

Adverse Events will be recorded.

4.2.3.5 Visit #6: Follow-up Visit (Week 24)

Radiographs- standing ap and lateral scoli xrays will be completed and centrally read by independent evaluators.
VAS back and leg, ODIv2.1a and SRS-22 scores will be collected
Current Pain medications/dosing will be collected.
Work Status will be recorded
Angular correction and gap will be measured.
Adverse Events will be recorded.

4.2.3.6 Visit #7: Follow-up visit (Week 52)

Radiographs- standing ap and lateral scoli xrays will be completed and centrally read by independent evaluators.
VAS back and leg, ODIv2.1a and SRS-22 scores will be collected
Current pain medications/dosing will be collected.
Angular correction and gap will be measured.
A CT scan will be taken to evaluate screw loosening and other measures of bone healing.
Adverse Events will be recorded.

4.2.3.7 Visit #8: Follow-up visit (Week 104)

Radiographs standing ap and lateral scoli xrays will be completed and centrally read by independent evaluators.
VAS back and leg, ODIv2.1a and SRS-22 scores will be collected
Current Pain medications/dosing will be collected.
Angular correction and gap will be measured.
Adverse Events will be recorded.

5. ADVERSE EVENTS (DEFINITIONS AND REPORTING)

All adverse events reported spontaneously by the subject/or in response to questioning or observation by the investigator will be recorded.

5.1 ADVERSE EVENT

An adverse event (AE) is defined as any unfavorable or unintended sign, symptom, or disease temporally associated with the use of the study products, or worsening of a pre-existing condition, whether or not it is considered related to the study treatment. All AEs and intercurrent illnesses must be recorded in the subject's medical records and on the CRF.

Adverse events will be defined as those events that occur after signing the informed consent until the final study visit. A description of the AE along with the onset date, end date, severity, action taken, treatment, outcome, likely cause, and relationship to the study products will be recorded in the CRF.

Local and systemic AEs associated with each treatment arm will be tabulated and compared. AEs will be elicited through direct questioning, subject reports, and physical examination.

An abnormal laboratory test result is not by itself considered to be an AE unless the Investigator considers the finding of clinical significance that should be reported in such a manner.

5.1.1 Reporting of Adverse Events

The Investigator will be responsible for assessing the relationship of the adverse event to the investigational product, and the seriousness and expectedness of the adverse event at the time of occurrence. A medically

qualified person appointed by the Sponsor will also assess this, once the Sponsor has been notified of an AE. All adverse events that occur during the trial will be documented on the supplied adverse event forms.

AEs and serious adverse events (SAEs) reported during the study, or SAEs reported within 30 days of the end of the study, will be followed to resolution of the AE/SAE or, within thirty days from the end of the study, a further and final assessment of the outcome will be made.

Each AE will be categorized as “serious” or “not serious” based on the definition of an SAE. An SAE is defined as an AE resulting in at least one of the outcomes described in Section 5.2.

The severity of AEs will be classified as “mild”, “moderate”, or “severe”, based on the following definitions:

- Mild: Awareness of sign, symptom, or event, but easily tolerated; does not interfere with usual daily activities or tasks.
- Moderate: Discomfort enough to cause interference with usual daily activity; may warrant therapeutic intervention.
- Severe: Incapacitating; inability to perform usual activities and daily tasks; significantly affects clinical status; requires therapeutic intervention.

AEs will be assigned a relationship (causality) to the study products. The Investigator will be responsible for determining the relationship between an AE and the study product. The type of event, organ system affected, and timing of onset of the event will be factors in assessing the likelihood that an AE is related to the treatment. Relationship of AEs to study products will be classified as follows:

- Not Related: No relationship exists between the AE and the treatment. The event is attributed to a pre-existing medical condition or an intercurrent event unrelated to the study product.
- Possibly Related: Follows the treatment, but may have developed as a result of an underlying clinical condition or treatments/interventions unrelated to the study product.
- Probably Related: Follows the treatment, but is unlikely to have developed as a result of the subject’s underlying clinical condition or other treatment or other interventions.
- Definitely Related: Follows the treatment and physical evidence shows a convincing relationship to the treatment.
- Unknown: Follows the treatment, but unable to determine the relationship to the treatment.

5.1.2 Subject Follow-up

Subjects who experience an AE will be followed until the AE has resolved, if possible.

5.2 SERIOUS ADVERSE EVENT

A SAE will be defined as any untoward medical occurrence that occur after signing the informed consent until the Final Evaluation that:

- Results in death,
- Is life-threatening,
- Requires inpatient hospitalization or prolongation of existing hospitalization,
- Results in persistent or significant disability/incapacity,
- Is a congenital anomaly/birth defect,
- Other (event not covered by SAE categories but in the investigator’s opinion, should be considered serious).

Important medical events that may not result in death, be immediately life threatening, or require hospitalization may be considered an SAE when, based upon medical judgment, if they may jeopardize the subject and require intervention to prevent one of the outcomes listed above.

5.2.1 Reporting Serious Adverse Events

The Investigator must report all SAEs (including any subject deaths) occurring during the study (from informed consent until the Final Evaluation). Once the Investigator becomes aware of an SAE, he/she must e-mail (preferred method of communication) or telephone the Sponsor within 24 hours:

**[name], M.D., Ph.D
Consultant Medical Officer**

**Telephone (home): [contact]
Telephone (Sweden; May through August):
[name]
Telephone (mobile): [contact]
Email: [contact]**

The Investigator is responsible for reporting all SAEs to the appropriate Institutional Review Board (IRB) in accordance with local laws and regulations. The Investigator is responsible for maintaining documentation in the study file that indicates the IRB has been properly notified.

5.3 UNANTICIPATED ADVERSE DEVICE EFFECT (UADE)

An unanticipated adverse device effect is defined as any serious adverse effect on health or safety, or any life-threatening problem or death caused by, or associated with, a device, if that effect, problem, or death was not previously identified in nature, severity, or degree of incidence in the investigational plan or application, or any other unanticipated serious problem associated with a device that relates to the rights, safety, or welfare of subjects.

5.3.1 Reporting UADEs

The Investigator must report all UADEs (including any subject deaths) occurring during the study (from informed consent until the Final Evaluation). Once the Investigator becomes aware of an UADE, he/she must e-mail (preferred method of communication) or telephone the Sponsor within 24 hours:

**[name], M.D., Ph.D
Consultant Medical Officer**

**Telephone (home) : [contact]
Telephone (Sweden): [name]
Telephone (mobile): [contact]
Email: [contact]**

6. STATISTICAL DESIGN

6.1 DESIGN

This is a parallel group, randomized, open, multicenter, prospective study in subjects with spinal deformities requiring a PSO procedure at a single level. Patients will be randomized 1:1 to receive either MONTAGE or no bone hemostat. Within each randomization study group, patients will be stratified according to their smoking status (non-smokers versus current smokers).

The primary objective of this study is the evaluation of post-operative blood loss in the week following surgery.

The secondary outcome will be the stability of the construct, as measured by the gap between the repaired osteotomy edges. In addition, observations will be made regarding whether the hardware repair has been maintained, and if the screws have loosened, and if the inserted rods are intact. Each repair complication will be categorized as belonging to one of the following groups: 1) hardware malplacement, 2) loosening or dislodgment, 3) nonunion or nonfusion with hardware fracture 4) nonunion or nonfusion without hardware fracture 5) peri-hardware fracture. These complications will be measured with imaging, including CT scans performed at 1-year. Fusion failure will be determined to be present if an area of perihardware lucency greater than 2 mm in thickness is present.

Malplacement of hardware will be considered present when an abnormal hardware position with hardware impingement on an important structure such as nerve or vessel is present.

Other secondary objectives will include:

- The formation of new bone at the osteotomy site, measured in mms at 1-year post surgery at the osteotomy site.
- VAS back and leg, Oswestry Disability Index (ODIv2.1a), and SRS-22 scores which will be recorded during the study and reported as outcomes scores, and compared between the two groups.
- Analysis of the MONTAGE/vertebral body interface, evaluating whether bony substitution has occurred at 1-year post-surgery. The presence or absence of bony resorption around the MONTAGE will also be reviewed.
- The use and type of antifibrinolytics will be compared between the two groups.

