The primary efficacy outcome variable for the study is the amount of post-operative bleeding compared between patients randomized 1:1 to MONTAGE or standard of care (no bone hemostat). Blood loss will be measured indirectly by formulae that provide an estimate through changes in hematocrit. A 2-sided “t” test will be used for the analysis.

Safety Endpoints:

Consistent with the standard of care, successful reconstruction of the osteotomy site requires observation of the residual angle of the osteotomy and any gap that may be present. In order to demonstrate that the use of Montage does not negatively impact the desired outcome, any residual gap will be measured in millimeters and compared between the groups. This will be done by including a CT scan performed at 1-year post surgery. A 2-sided “t” test will be used for the analysis.

NRS back pain and NRS leg pain, SRS-22 and Oswestry Disability Index (ODIv2.1a) will be compared between the two groups and also reported as secondary outcome scores. Descriptive statistics will be reported.

PROTOCOL APPROVAL

Date
.....
.....
Date
.....
[name], Ph.D
Consultant Medical Officer
ABYRX

INVESTIGATOR AGREEMENT

The signing of this protocol by the Investigator signifies that the contents have been laid down in full agreement and that the trial will be conducted according Good Clinical Practice and to the procedures described.

.....
Date
<Investigator>

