3. TRIAL SUBJECT POPULATION

3.1 NUMBER OF SUBJECTS

A multicenter study will be undertaken in the US, with up to 4-6 centers contributing 50 patients (maximum of 20 patients per center). A sample size of 25 randomly assigned patients per study group (50 subjects in total) was calculated to detect a clinically significant treatment effect of MONTAGE (90% power; alpha = 0.05, 2-sided; 10% lost-to-follow up). This calculation was performed with the assumption that subjects within the control group lose on average 1,500 mL (+/- 500mL) of blood postoperatively while subjects within the treatment group will lose 1,000 mL of blood postoperatively.

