4. TRIAL DESIGN AND METHODOLOGY

4.1 TRIAL DESIGN

This study will be an open, prospective, multicenter, randomized, and controlled study to evaluate the effects of MONTAGE® on blood loss and maintenance of the PSO corrective surgical procedure. Patients will be randomized to receive either standard of care (no bone hemostat) or MONTAGE. Within each study group, patients will be stratified according to their smoking status (non-smokers versus current smokers).

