6.2 SAMPLE SIZE

A total of 50 subjects will be recruited to this study, with 1:1 randomization, stratified to ensure equal distribution of smokers and non-smokers within each group.

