6.3 ANALYSIS PLAN

The statistical analysis will be performed in conjunction with Abyrx. Analyses will be conducted on the Intention-to-Treat population (ITT), with additional Per Protocol analyses. All significance tests will be two-sided; p-values will be provided with $P(H_0) < 0.05$ indicating a significant difference.

All other analyses with respect to demographic and clinical parameters will be reported with descriptive statistics.

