6.3.2 Secondary Variables and Analyses

Several secondary analyses will be carried out; the results of any secondary analyses are exploratory.

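### Randomisation is stratified by smoking status, but the primary t test leaves the stratum out; adding it costs one degree of freedom and can only help if smoking predicts blood loss

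*Combined protocol and SAP*

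**What the plan says.** - **Stratification.** Section 4.1: "Within each study group, patients will be stratified according to their smoking status (non-smokers versus current smokers". Section 6.1 repeats this almost word for word: "Within each randomization study group, patients will be stratified according to their smoking status (non-smokers versus current smokers". Section 6.2 links it to the allocation: 50 subjects, 1:1, "stratified to ensure equal distribution of smokers and non-smokers within each group".
- **Allocation mechanics.** Section 4.2.2 says that the centre contacts the central data repository and that "random assignment will be generated by computer". It mentions neither strata nor blocks.
- **Primary analysis.** The Summary, under the efficacy endpoint, says "A 2-sided “t” test will be used for the analysis". Section 6.3 adds ITT and per-protocol analyses and says "All significance tests will be two-sided", but names no model, covariate or stratum. Section 6.3.2 adds only that "the results of any secondary analyses are exploratory".
- **Multivariate combination.** The one in section 1.4 is exploratory. It combines measures of blood loss and does not adjust for smoking.
- **Sample size.** Section 3.1 gives 25 per group for "90% power; alpha = 0.05, 2-sided; 10% lost-to-follow up", with mean losses of 1,500 mL (+/- 500 mL) and 1,000 mL.

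**The concern.** The plan balances the arms on smoking and then analyses the data as if it had not. When a factor that predicts the outcome is balanced between arms, it no longer contributes to the random error of the treatment difference. A t test that ignores the factor still counts its variance in the standard error, so that standard error is too large.

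At stake are some power and some width of the confidence interval in a 50-patient trial. The test also becomes conservative, with a true type I error below its nominal 5%. The estimate stays unbiased and a false claim of benefit becomes no more likely. If smoking does not predict blood loss, nothing is lost by leaving it out.

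**Working it through.** **1. The plan's own figure.** Inputs from section 3.1: difference 500 mL, SD 500 mL (reading +/- 500 mL as the SD), two-sided alpha 0.05, power 90%, 10% loss.

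n per arm = 2(1.960 + 1.282)² × 500²/500² = 21.0, rounded up to 22. Then 22/0.9 = 24.4, rounded up to 25. The stated 25 per group reproduces. Exact t-test power is 90.0% at 22 per arm and 91.2% at 23 per arm.

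**2. What the t test leaves in.** Let R² be the share of within-arm variance explained by smoking. With balance within strata:

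- true variance of the treatment difference = 500²(1 − R²)(1/n₁ + 1/n₂)
- variance the t test works with, on average = 500²(1/n₁ + 1/n₂)

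The adjusted interval is therefore narrower by a factor of about √(1 − R²): 0.975 at R² = 0.05, 0.949 at 0.10, 0.917 at 0.16 and 0.866 at 0.25.

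**3. Direct cost of the extra term.** Smoking has two levels, so it takes one degree of freedom. With 22 per arm, the degrees of freedom go from 42 to 41 and the critical t from 2.0181 to 2.0195. At R² = 0 with perfect balance, power goes from 89.97% to 89.94%.

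**4. Simulation with realistic balance.** 20,000 trials per setting; 50 randomised and 45 evaluable; total SD 500 mL; effect 500 mL; blocks of 4 within stratum; half of patients smokers. The smoker/non-smoker gap is 500√(R²/(p(1 − p))), which is 1,000√R² at p = 0.5.

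| R² | Gap (mL) | Power, t test | Power, adjusted | CI width ratio | Type I, t test | Type I, adjusted |
|---|---|---|---|---|---|---|
| 0 | 0 | 90.2% | 90.1% | 1.002 | 5.0% | 5.1% |
| 0.05 | 224 | 90.7% | 91.4% | 0.976 | 4.6% | 5.1% |
| 0.10 | 316 | 91.7% | 93.2% | 0.950 | 4.1% | 4.9% |
| 0.16 | 400 | 91.9% | 94.5% | 0.916 | 3.5% | 5.0% |
| 0.25 | 500 | 93.2% | 96.5% | 0.864 | 2.7% | 5.0% |

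The width ratios agree with step 2. With 20% smokers the power gains are similar: 90.8% to 91.7% at R² = 0.05, and 91.2% to 92.9% at R² = 0.10.

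**5. In millilitres.** With 22 and 23 evaluable, the t test's half-width is about 2.017 × 500 × √(1/22 + 1/23) = 301 mL. Adjustment saves about 7 mL at R² = 0.05 (2.4%) and about 15 mL at R² = 0.10 (5.0%).

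**6. If allocation is not balanced within strata.** Same settings, no stratification or blocking by smoking:

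| R² | Power, t test | Power, adjusted |
|---|---|---|
| 0 | 90.6% | 89.9% |
| 0.05 | 90.5% | 91.4% |
| 0.10 | 90.4% | 92.4% |
| 0.16 | 90.5% | 94.2% |
| 0.25 | 90.5% | 96.3% |

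The t test's type I error is then 4.9% to 5.1% throughout. The 0.7-point loss at R² = 0 comes mainly from chance imbalance in smoking between the arms.

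**The case against.** The strongest reply is that nothing here is wrong. A prespecified unadjusted t test is valid, the sample size supports it, and a conservative test cannot manufacture a benefit. The gain rests on an R² that the documents do not supply: the background on blood loss in section 1.3 never mentions smoking, no reason for stratifying is given, and zero is a possible value. At moderate values the gain is 7 to 15 mL of half-width against an assumed effect of 500 mL. The larger gains need a smoking gap of 400 to 500 mL, close to or equal to the treatment effect itself. Nor is adjustment strictly free: if allocation is not balanced on smoking, it costs about 0.7 power points at R² = 0 and pays only above an R² somewhere between 0.02 and 0.05. The wording in sections 4.1 and 6.1 is ambiguous, and section 4.2.2 mentions no strata.

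All of this stands as a limit on the size of the point, and it is why the allocation wording needs clarifying as well. It does not remove the point. Section 6.2 states that the randomisation is stratified so as to balance smoking, and under that design the cost of adjustment is negligible. The small loss without balance would arise only if the design did not deliver what section 6.2 promises.

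**Conclusion.** The point holds as a low-cost improvement, not as a defect that threatens the conclusion. The design stratifies on smoking, and no part of the primary analysis uses it.

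- With blocking within strata, prespecified adjustment gains 0 to about 1.5 power points for R² up to 0.10, and 2.6 to 3.3 points in the simulated cases with gaps of 400 to 500 mL.
- It keeps the type I error close to 5%, where the t test falls to 4.1% at R² = 0.10 and 2.7% at R² = 0.25.
- The worst case is a loss of 0.1 to 0.2 points with blocking, or about 0.7 without it.

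These sizes assume an SD of 500 mL, 45 evaluable patients, and stated values for R², the share of smokers and the block size. The existence of a gain depends on smoking predicting blood loss, which the documents do not address. The sample size need not change.

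**What to change.** In the Summary and section 6.3, replace the primary test with:

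> The primary analysis will be a linear model of postoperative blood loss on treatment and the smoking stratum used at randomization. The adjusted mean difference with 95% CI and two-sided p-value will be reported. The unadjusted two-sided t test will be a sensitivity analysis.

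In sections 4.1, 4.2.2 and 6.1, state that assignment is made separately within each smoking stratum, and whether blocks are used, instead of describing stratification inside each study group.

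The cost is three sentences plus the clarification, and one degree of freedom. No new data are needed, because the Appendix I schedule already records smoking status at baseline. The change should be made before outcome data are seen: in an open trial, an adjustment chosen afterwards could look like picking the favourable analysis.

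### Centre is used in neither the allocation nor the primary test, although one of 4-6 centres may supply 20 of the 50 patients: a loss of precision and exposure to chance imbalance, not a bias

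*Combined protocol and SAP*

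**What the plan says.** - **Balancing factor.** Section 6.1 states: "Within each randomization study group, patients will be stratified according to their smoking status (non-smokers versus current smokers". Sections 4.1 and 6.2 also name smoking and nothing else.
- **Allocation.** Section 6.1: "Patients will be randomized 1:1 to receive either MONTAGE or no bone hemostat". Under 4.2.2 the centre contacts a central repository after submitting pre-operative data, and "random assignment will be generated by computer". No centre factor, block size or minimisation is given.
- **Centres.** Section 3.1: "up to 4-6 centers contributing 50 patients (maximum of 20 patients per center".
- **Primary analysis.** The Summary specifies a two-sided t test. Section 6.3 adds no covariate, for centre or for smoking.
- **Sample size.** Section 3.1: "A sample size of 25 randomly assigned patients per study group (50 subjects in total", with "90% power; alpha = 0.05, 2-sided; 10% lost-to-follow up".

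**The concern.** One centre may contribute 20/50 = 40% of the patients, and nothing keeps the arms level within it. If mean blood loss differs between centres, an uneven split of a large centre passes straight into the unadjusted treatment difference, and the remaining centre variation stays in the error term.

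It is plausible that centres differ. The formula in 4.1.1 counts intra-operative loss, transfused red cells and Cellsaver volume, while MONTAGE is applied only just before the osteotomy is closed (4.2, 4.2.3.1). The measured loss therefore includes bleeding from before treatment. Antifibrinolytic use is recorded, but no rule makes it uniform across sites. At stake are precision and how readily the result can be read: a centre term added after an uneven split has been seen would look data-driven.

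**Working it through.** **1. The plan's own sample size.** Inputs from 3.1: "subjects within the control group lose on average 1,500 mL (+/- 500mL) of blood postoperatively" (500 mL read as the SD), "subjects within the treatment group will lose 1,000 mL of blood postoperatively" (difference 500 mL), power 90%, two-sided alpha 0.05, 10% loss.

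n per arm = 2 × (1.960 + 1.282)² × (500/500)² = 21.02, rounded up to 22. Then 22/0.90 = 24.4, rounded up to 25 per arm. This reproduces the plan. By the noncentral t, power is 0.900 at 22 per arm and 0.934 at 25.

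**2. How often a large centre splits unevenly.** Take a 20-patient centre, 25:25 overall, allocation ignoring centre. The number of its patients given MONTAGE is hypergeometric (N = 50, K = 20, n = 25), with mean 10 and SD 1.75.
- P(12:8 or worse, either direction) = 0.387
- P(13:7 or worse) = 0.148
- P(15:5 or worse) = 0.009

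**3. What such a split does.** Shift = centre difference × (13 − 7)/25 = 0.24 × centre difference. The centre difference is not in the documents and is assumed:
- 250 mL gives 60 mL (12% of the 500 mL target)
- 500 mL gives 120 mL (24%)

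The standard error of the difference is 500 × √(2/25) = 141 mL, so these shifts are 60/141 = 0.42 and 120/141 = 0.85 standard errors.

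**4. Simulation over an assumed ICC.** 20,000 trials of 50 evaluable patients, total SD held at 500 mL, centre sizes 20/15/10/5, five of 10, or 20/10/8/6/4/2. The ICC is the assumed share of variance due to centre. In the last two columns allocation is 1:1 within centre and centre is in the model. Ranges cover the three layouts.

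| ICC | 95th percentile of absolute shift, as planned (mL) | SD of estimate, as planned (mL) | Power, as planned | SD, centre in both steps (mL) | Power, centre in both steps |
|---|---|---|---|---|---|
| 0 | 0 | 142-143 | 0.93-0.94 | 141-142 | 0.93-0.94 |
| 0.05 | 56-59 | 140 | 0.94 | 138 | 0.94-0.95 |
| 0.1 | 78-84 | 138-140 | 0.94 | 133-136 | 0.95 |
| 0.2 | 110-118 | 138-139 | 0.94 | 126-127 | 0.97 |
| 0.3 | 137-145 | 136-137 | 0.94-0.95 | 118-119 | 0.98-0.99 |

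The mean shift is zero (within 1 mL) throughout. Type I error of the planned t test is 0.047-0.053.

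**5. Variants.**
- Minimisation on centre and smoking with a random element, both factors in the model (assumed: favoured arm with probability 0.8, a quarter of patients smokers, no smoking effect): type I error near 0.05, power about 0.92-0.93 at ICC 0 and 0.98 at ICC 0.3, SD 119-122 mL at ICC 0.3.
- Balancing on centre but keeping the plain t test makes the test conservative: type I error 0.033-0.036 at ICC 0.2 and 0.026-0.032 at ICC 0.3. The two changes belong together.
- Centre in the model only, allocation as planned: power 0.90-0.92 at ICC 0; SD 131-133 mL at ICC 0.2 and 123-124 mL at ICC 0.3.

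**The case against.** The strongest reply is that central 1:1 randomisation is itself the protection. Between-centre variation is already in the standard error, so the p-value and interval allow for chance imbalance. This stands. A reader might infer that the estimate is biased or the test invalid; the zero mean shift and the type I error near 0.05 show otherwise. A reader might also infer that power is overstated. If the 500 mL SD already includes centre variation, it is not.

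The 60-120 mL figure also combines unfavourable conditions: a centre at the 20-patient cap, a 13:7 split, and a centre difference of up to one full SD that no section gives. The probability of 0.148 covers both directions; against either given arm it is 0.074. This stands too, and is why the shift is set against the standard error and a range of ICCs.

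No section calls blood loss operator-dependent; that is inferred from the formula. The formula adds back transfused cells and Cellsaver volume, which partly accounts for those practices. Sites also share more than the teaching video in 4.2: single-level PSO (3.3.1), exclusion of bleeding disorders (3.3.2) and one formula (4.1.1).

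Finally, in an open trial each site sees its own assignments, so leaving centre out makes the next one harder to guess. That is a real advantage, and it bears on the method of balancing. None of this gives a reason to leave centre out of the analysis when patients are clustered in so few sites.

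**Conclusion.** The omission is confirmed, and its consequence is modest. The planned comparison is valid. What is lost is precision and protection against an uneven centre split in this single trial. At ICC 0.3 the SD of the estimate would fall from about 136-137 mL to 119-122 mL with minimisation and the matching model; at ICC 0.05 there is little to gain. The size rests on an assumed ICC or centre difference, on exactly 25 patients per arm, and on 500 mL being the total SD. This is a worthwhile, inexpensive improvement rather than a defect that threatens the conclusion.

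**What to change.** **Allocation (4.2.2, 6.1, 6.2).** Have the central computer balance on centre and smoking by minimisation with a random element. Crossing the two factors would give 8-12 cells for 50 patients, about 4-6 per cell, which is too sparse for ordinary stratified blocks.

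**Analysis (6.3 and Summary).** Replace the plain t test with a linear model for treatment, centre and smoking. Fix a rule for pooling very small centres before data review.

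**Cost.** Reprogramming of the central system; 4-6 degrees of freedom (3-5 for centre, 1 for smoking); about 1 point of power if centres do not differ; and some added predictability within centre, limited by the random element. N is unchanged.

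**If enrolment has begun.** Pre-specify the model change alone. This costs about 2-4 points of power if centres do not differ. By the SDs above, it recovers roughly half of the available gain in precision at ICC 0.2 and about three quarters at ICC 0.3.
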